6.7 BCSS

The BCSS is a daily patient-reported outcome measure that was designed as a daily diary in which patients are asked to report the severity of three symptoms: breathlessness, cough and sputum (11).

Each symptom is represented by a single item which is evaluated on a 5-point scale ranging from 0-4, with higher scores indicating more severe symptoms. A mean decline of 1 point on the BCSS total scale signifies a substantial reduction in symptom severity. This questionnaire should only be completed if an approved translation in the language required by the patient is available. If an approved translation is not available, this assessment will not be conducted and will not be recorded as a protocol deviation.

This assessment should be carried once a day from Day 1 until Day 28 and then on Day 60 and Day 90 (see Appendix C).

- This assessment should be carried out at approximately the same time each day.
- This assessment should be completed via patient interview. Trained staff should read each question verbatim and ask the patient to answer using the words and the number (e.g. “none – unaware of coughing” and “0”).
- For patients discharged home during treatment, the site/study staff will ask the patient the questions by telephone/video link and the patient should have a copy of the BCSS questionnaire for reference whether they are hospitalised or discharged.
- This is a patient reported outcome, so for patients that are unable to complete the BCSS due to their medical condition i.e. if they are receiving ventilation, the reason for non-completion should be recorded in the source documents.
- The applicable score (number) for each question should be recorded in the source documents as well as the date, time and method of assessment.

6.8 Vital Signs

Vital signs include temperature, respiratory rate, heart rate and blood pressure should be recorded daily whilst the patient is hospitalised. Vital signs should be assessed at the same time as the daily physical examination. When the patient is discharged home vital sign assessments will not be recorded.

Blood pressure and pulse should be measured in the supine position and it is recommended that the patient should have rested quietly for at least 3 minutes prior to the measurement.

6.9 NEWS2

The data required for NEWS2 will be collected by the site staff and NEWS2 will be calculated by the Sponsor.

NEWS2 is a tool developed by the Royal College of Physicians, which improves the detection and response to clinical deterioration in adult patients and is a key element of patient safety and improving patient outcomes (12).

NEWS2 is based on a simple aggregate scoring system in which a score is allocated to physiological measurements, already recorded in routine practice, when patients present to, or are being monitored in hospital.

Six simple physiological parameters form the basis of the scoring system:

1. Respiration rate
2. Oxygen saturation
3. Any supplementary oxygen
4. Temperature
5. Systolic blood pressure
6. Heart rate
7. Alert, Voice, Pain, Unresponsive.

The highest NEWS2 score for each calendar day should be collected. The highest NEWS2 score will be recorded daily, for each calendar day, whilst the patient is hospitalised. When the patient is discharged home, NEWS2 will not be recorded.

6.10 Quality of Life Measured Using EQ-5D-5L

The EQ-5D-5L health-related quality of life questionnaire will be completed on Day 0, Day 7, Day 15, Day 28, Day 60 and Day 90 for all patients (see Appendix D).

In addition, the mobility, self-care and usual activities dimensions of the questionnaire will be assessed daily from Day 1 to Day 35.

The EQ-5D-5L provides a simple descriptive profile and a single index value for health status. The EQ-5D-5L self-rated questionnaire includes a visual analogue scale (VAS), which records the respondent's self-rated health status on a graduated (0–100) scale, with higher scores for higher health-related quality of life. It also includes the EQ-5D-5L descriptive system, which comprises 5 dimensions of health: mobility, self-care, usual activities, pain/discomfort, and anxiety/depression. The responses record five levels of severity (no problems/ slight problems/ moderate problems/ severe problems/ extreme problems) within a particular EQ-5D dimension. This questionnaire should only be completed if an approved translation in the language required by the patient is available. If an approved translation is not available, this assessment will not be conducted and will not be recorded as a protocol deviation.

6.11 COVID-19 symptom assessment

The presence of COVID-19 symptoms will be assessed as per the study schedule.

A checklist/worksheet will be provided to study site staff to document the COVID-19 symptoms. The questionnaire is provided in Appendix F.

6.12 Assessment of Long-COVID-19 symptoms

Assessment of long-COVID-19 symptoms will be performed on Day 15, Day 28, Day 60 and Day 90. The following patient reported outcome measures will be used:

- General Anxiety Disorder 7 Questionnaire (GAD-7)
- Patient Health Questionnaire-9 (PHQ-9)
- Functional Assessment of Chronic Illness Therapy (FACIT) - Fatigue Scale (Version 4)
- Brief Pain Inventory (Short Form)

The questionnaires are included in Appendix E and should only be completed if approved translations in the language(s) required by the patient(s) are available. If approved translations are not available, these assessments will not be conducted and will not be recorded as protocol deviations.

6.13 Samples for Laboratory Assessment

6.13.1 Urine Pregnancy Test

Early detection pregnancy strips (minimum detection 10 MIU human chorionic gonadotrophin) will be used on Day 0.

Urine pregnancy testing is not required for women who are not of child-bearing potential. Women not of childbearing potential are defined as women who are either permanently sterilised (hysterectomy, bilateral oophorectomy, or bilateral salpingectomy), or who are postmenopausal.

Women will be considered postmenopausal if they have been amenorrhoeic for 12 months prior to the planned date of randomisation without an alternative medical cause. The following age specific requirements apply:

- Women <50 years old would be considered postmenopausal if they have been amenorrhoeic for 12 months or more following cessation of exogenous hormonal treatment and if FSH levels are in the postmenopausal range. If the FSH result is not available at the time of randomisation, the patient must have a negative pregnancy test and agree to use approved contraceptive method. The patient must have been using this contraceptive method for a period of 3 month prior to randomisation.
- Women ≥ 50 years old would be considered postmenopausal if they have been amenorrhoeic for 12 months or more following cessation of all exogenous hormonal treatment.

6.13.2 Blood Sample for Immunogenicity Testing

A blood sample will be taken as per the study schedule for immunogenicity testing. This will be completed in all sites and for all patients, where collection of samples is feasible. If a site is not able to participate in immunogenicity sample collection, this will not preclude them from participation in the study. The sample will require processing to obtain serum which is required for the analysis and analysis testing will be completed using validated methods. A laboratory manual describing the requirements for the blood sample and the processing of the sample will be provided separately by the Sponsor (or delegate).

Immunogenicity will be determined by the presence of anti-drug antibodies (ADAs). A tiered analysis approach will be followed, whereby samples positive at the screening step will be confirmed for ADA presence. The confirmed positive samples will then be assessed for ADA titre and the presence of neutralising antibodies.

6.13.3 CCI

CCI

CCI

6.14 Concomitant Medications

Medications taken by the patient at the time of informed consent should be recorded in the source data. After this, patients will be asked at each visit if they have taken any new concomitant medications or changed any current medications. Alternatively, information can be obtained from the patient's hospital prescription record. The dosage information, dates of administration and reasons for use will be recorded.

Any other medications which are considered necessary for the patient's welfare should be given at the discretion of the Investigator.

Special care will be taken in questioning the patients on any possible self-medication.

SOC medications for the treatment of COVID-19 (e.g. remdesivir or dexamethasone) can be administered, as required. SOC should be recorded as concomitant medications.

Oxygen therapy will be recorded as concomitant medication.

6.15 Prohibited Medications

Interferons have been reported to reduce the activity of hepatic cytochrome P450 dependent enzymes in humans and animals. Caution should be exercised with patients who are taking medicinal products that have a narrow therapeutic index and are largely dependent on the hepatic cytochrome P450 system for clearance (e.g. some classes of antidepressants). Investigators are able to enrol these patients to the study but should be aware of the possible contraindication.

Patients who have received a prior SARS-CoV-2 vaccination may be enrolled into the study. However, patients enrolled into the study should be advised to refrain from receiving vaccinations, including SARS-CoV-2 vaccinations, during the treatment and follow-up phase up to Day 35, as these could interfere with study assessments.

6.16 Co-Enrolment into Additional Interventional Studies

Co-enrolment into other interventional studies during the treatment and follow-up phases up to Day 35 should be avoided, as it could interfere with study assessments. Co-enrolment into any study must be discussed with the Medical Monitor to clarify whether co-enrolment is permitted.

7 ADVERSE EVENT REPORTING

7.1 Adverse Events

An AE is defined as any untoward medical occurrence in a clinical trial patient during the study; the event does not necessarily have a causal relationship with that treatment. An AE can therefore be any unfavourable and unintended sign (including any clinically significant abnormal laboratory finding), symptom or disease, temporally associated with the use of a medicinal product.

AEs may include the following:

- Apparently unrelated illnesses, including the worsening of a pre-existing illness.
- Injury or accidents.

Patients will be asked about AEs at every study visit. General, non-directed questioning will be used to elicit reports of AEs. If a patient is seen by a physician not involved with the study in relation to an AE, the Investigator should make every effort to contact the treating physician in a timely manner in order to obtain all information necessary to facilitate appropriate reporting of the event.

- The terms ‘COVID-19’ or ‘SARS-CoV-2’ should not be recorded as an AE.
- Individual symptoms related to COVID-19/SARS-CoV-2 infection (e.g. fever, breathlessness, fatigue) present at study entry should not be reported as AEs.
- Worsening of symptoms related to COVID-19/SARS-CoV-2 infection should be reported as AEs if, in the investigators’ opinion, the symptoms are clinically significant or lead to treatment.
- New symptoms related to COVID-19/SARS-CoV-2 infection that start after the initiation of study treatment should be reported as AEs.

7.2 Treatment-Emergent Adverse Events

A treatment-emergent adverse event (TEAE) is an AE that is new in onset, or is a pre-existing condition that is aggravated in severity or frequency, and occurs after the administration of the first dose of study medication. TEAEs include any clinically significant change from baseline readings in any of the study assessments.

Any abnormal result from study assessments will be recorded as an AE, if they result in study withdrawal, are associated with accompanying symptoms, lead to treatment, lead to further diagnostic tests, or is considered by the Investigator to be of clinical significance. These should be recorded in the source documents.

7.3 Serious Adverse Event

An SAE, according to ICH GCP, is any AE that meets any of the following outcomes:

- Results in death.
- Is life-threatening (i.e. at immediate risk of death).
- Requires in-patient hospitalisation or prolongation of existing hospitalisation.
- Results in persistent or significant disability or incapacity.
- Consists of a congenital anomaly or birth defect.

AEs that may not result in death, may not be life-threatening, or do not require hospitalisation may be considered SAEs when, based upon appropriate medical judgment, they may jeopardise the patient or may require medical or surgical intervention to prevent one of the outcomes listed above. These events must be reported in the same manner as SAEs.

Deterioration of a patient's condition requiring admission to the intensive care unit or invasive mechanical ventilation, (whichever happens first) must be reported as an SAE.

Elective and pre-planned surgeries will not be reported as SAEs. Such procedures should be recorded as part of the medical history.

7.4 Assessment of Adverse Event

The Investigator will assess every AE to determine if it is serious or not (see Section 7.3 for definition criteria). This assessment will determine the reporting procedures to be followed.

7.4.1 Relationship to Study Medication

Investigators (or delegates) need to assess the causality and severity (intensity) between the study medication and/or concomitant medication and the AE; this information will be recorded in the source documents.

7.4.1.1 Causality

Causality is the relationship between the study medication and the occurrence of the AE. Determination of causality is based on the Investigator's clinical judgment regarding the likelihood that the study medication caused the AE and may include consideration of some or all of the following factors:

- Alternative possible causes of the AE, including the patient's underlying disease or co-morbid conditions, other drugs, other host and environmental factors.
- The temporal sequence between the study medication exposure and the AE.
- Whether the clinical or laboratory manifestations of the AE are consistent with known actions or toxicity of the study medication.

Investigators need to assess the relationship of AEs to the study medication by consulting the IB and using the following definitions:

Definitely related: A causal relationship of the onset of the event relative to administration of the study medication and there is no other cause to explain the event.

Probably related: A causal relationship is clinically/biologically reasonable relative to the administration of the study medication and the event is more likely explained by exposure to the study medication than by other factors or causes.

Possibly related: A causal relationship is clinically/biologically reasonable relative to the administration of the study medication, but the event could have been due to another equally likely cause.

Unlikely to be related: A causal relationship is considered unlikely to be related to use of the study medication if there are factors (evidence) explaining the occurrence of the event (e.g., progression of the underlying disease, concomitant medication more likely associated with the event) or a convincing alternative explanation for the event.

Unrelated: A causal relationship is not reasonably related in time to the administration of the study medication, or exposure to the study medication has not occurred.

7.4.1.2 Severity

Severity (intensity) should be assessed according to the following definitions:

Mild: The patient is aware of the event or symptom, but the event or symptom is easily tolerated, causing minimal discomfort to the patient. The event or symptom should not interfere with everyday activities.

Moderate: The patient experiences sufficient discomfort to interfere with or reduce normal everyday activities, but responds to symptomatic therapy or rest.

Severe: Significant impairment of functioning: the patient is unable to carry out normal everyday activities despite symptomatic therapy and/or the patient's life is at risk from the AE.

Note the distinction between the gravity and the severity (intensity) of an AE. Severe is a measure of intensity: thus, a severe reaction is not necessarily a serious reaction. For example, a headache may be severe in intensity, but would not be classified as serious unless it met one of the criteria for SAEs listed above.

7.5 Discontinuation of Study Medication Due to an AE

Study medication may be discontinued (temporarily or permanently) in response to an AE at any time at the discretion of the patient and/or the Investigator. This will be reported on the AE page in the eCRF.

The Sponsor (or delegate) will be informed as soon as possible of any patient for whom permanent discontinuation of study medication occurs.

7.6 Pregnancy

Pregnancy itself is not an AE unless there is a suspicion that the study medication may have interfered with the effectiveness of a contraceptive medication. However, if a female patient becomes pregnant during the conduct of the study, study medication will be discontinued immediately, and the Sponsor (or delegate) should be notified within 24 hours using the Pregnancy Report Form. Follow-up information regarding the outcome of the pregnancy and any foetal or neonatal sequelae should be obtained and documented. For all pregnant patients, on behalf of the Sponsor, study staff will discuss referral for specialist counselling on the possible risks to the unborn baby, and arrangements will be offered to monitor the health of both the patient and the unborn baby.

7.7 Adverse Events Recording and Reporting

7.7.1 Reporting of Adverse Events

All AEs and TEAEs will be reported from the day informed consent is obtained until 28 days after the last administration of the study medication. This includes AEs reported as a result of study procedures.

All AEs and TEAEs occurring during the study assessed by the Investigator (or delegate) as definitely, probably or possibly related to the study medication are to be followed up until resolved or judged to be no longer clinically significant, or until they become chronic or stable to the extent that they can be fully characterised (all follow-up results are to be reported to the sponsor or delegated Clinical Research Organisation [CRO] if requested).

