5.3.4 Follow-up

All follow-up assessments can be either done face-to-face if the patient remains in hospital or via telephone/video call if the patient has been discharged from hospital as per the study schedule.

Days 16 to 28

WHO OSCi, BCSS, the mobility, self-care and usual activities dimensions of EQ-5D-5L, NEWS2, COVID-19 symptoms, AEs, SAEs, and concomitant medications should continue to be collected on a daily basis from the patient. In addition, the EQ-5D-5L (complete questionnaire) should be completed and long- COVID-19 assessment should be performed on Day 28. For patients who have been discharged, assessments should be performed via telephone/video link, if possible.

NEWS2 will only be assessed if the patient remains in hospital. If the patient has been discharged from hospital NEWS2 will not be assessed. For hospitalised patients, if the components of NEWS2 have already been assessed on the day of the visit, this data can be used on the study to avoid the same procedures being conducted twice. The highest NEWS2 score for each calendar day should be collected.

Days 29 to 35

WHO OSCI, COVID-19 symptoms, the mobility, self-care and usual activities dimensions of EQ-5D-5L, AEs, SAEs, and concomitant medications should continue to be collected (as per Sections 7.7.1 and 7.7.2) on a daily basis until (and including) Day 35.

Days 36 to 90

Blood sample for immunogenicity testing should be obtained from the patient (all sites/patients, where collection is feasible) on Day 44 (+/- 5 days).

Updates to ongoing AEs and SAEs will be collected at Days 44, 60, and 90, and at any unscheduled study visits during this period as per Section 7.7.1 and 7.7.2.

New AEs and SAEs will be collected up to 28 days after the last dose of study medication and documented at the next scheduled or unscheduled study visits as per Section 7.7.1 and 7.7.2.

All concomitant medications will continue to be recorded until study completion.

In addition, BCSS, EQ-5D-5L (complete questionnaire), COVID-19 symptoms and long-COVID-19 assessments should be performed on Day 60 (-2 to +5 days) and Day 90 (-2 to +5 days).

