7.8 Reporting of Serious Adverse Events

All AEs assessed as serious by the Investigator (or delegate) according to the criteria specified should be reported and recorded on a SAE form.

SAEs should be reported by the Investigator (or delegated person) to the Sponsor (or delegate), using the SAE report form provided, immediately (and not later than 24 hours) of a member of the site staff becoming aware of the event, whether or not the event is considered to be related to study medication. This initial report can be made by telephone or in writing. If the initial SAE report is made by telephone, a written report signed by the Investigator (or delegate) must be submitted immediately (and not later than 24 hours from the start of the event).

All SAEs will be reported from the day informed consent is obtained until 28 days after the last administration of the study medication. SAEs are to be followed until resolution regardless of whether the patient is still participating in the study.

Resolution means:

- The patient has returned to their baseline condition or the Investigator does not expect any further improvement or worsening of the event, or
- The SAE is deemed medically insignificant by the Investigator, or
- The SAE is resolved with residual effects.

Details of the contact numbers for SAE reporting can be found in the Investigator's Site File.

In addition to informing the Sponsor, the Investigator at the study site should notify the host organisation (e.g. Research and Development [R&D]) or any other department as required by local regulations if applicable.

The Sponsor will be responsible for informing the following within the stipulated reporting timelines:

- The Chief Investigator and site investigators
- Institutional Review Board/Independent Ethics Committee (IRB/IEC), and
- The appropriate local regulatory authority

The sponsor will comply with country-specific regulatory requirements relating to safety reporting to the regulatory authority, IRB/IEC, and investigators.

Copies of all correspondence relating to the reporting of SAEs should be maintained in the Investigator Site File and provided to the Sponsor (or delegate). The Investigator will be informed by the Sponsor (or delegate) of any SAEs from other Investigators or clinical studies which have safety implications.

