#### 5.3.1.5 *Death within 35 days of First Dose or Randomisation*

Deaths will be identified by an OSCi score of 8 at any post baseline assessment up to and including Day 35, a fatal Adverse Event (AE) on or before Day 35 or withdrawal due to a fatal AE on or before Day 35.

Patients who die after Day 35 will be considered alive for the derivation of death within 35 days of first dose or randomisation.

Day 35 will be determined by the study schedule, which may be more than 35 days after randomisation if randomisation occurs before Day 1.

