### 10.1 Adverse Events

Adverse events will be recorded from the time informed consent is given 28 days after the last administration of the study medication. All AEs will be coded using the latest available version of the MedDRA and will be categorized by intensity (mild/moderate/severe) and relationship (unrelated/unlikely to be related/possibly related/probably related/definitely related).

A treatment-emergent adverse event (TEAE) is defined as any event not present prior to the administration of study drug or any unresolved event already present before administration of study drug that worsens in intensity following exposure to the treatment. Where dates are missing or partially missing, AEs will be assumed to be treatment-emergent unless they clearly started prior to treatment (as indicated by the month/year if the day is missing etc.).

Summary tables will contain the cumulative incidence rate and the number of events where applicable. A subject who has multiple events in the same SOC and PT will be counted only once in the subject counts but all events will be included. Adverse event summaries will be ordered by the international SOC order ([Appendix III](#)) and decreasing frequency of PT within SOC, in the active arm overall column.

Summaries of TEAEs by SOC and PT will include the following:

- Incidence of TEAEs
- Incidence of serious TEAEs
- Incidence of serious related TEAEs
- Incidence of TEAEs by relationship
- Incidence of TEAEs by severity
- Incidence of TEAEs leading to discontinuation
- Incidence of TEAEs leading to death
- Incidence of related TEAEs leading to death.
- Incidence of TEAEs of special interest.
- 

An adverse event summary will summarise the number of TEAEs in each of the above categories alongside 95% Newcombe confidence intervals for the differences in proportions between treatment arms.

Summaries of TEAEs by PT will include the following:

- Incidence of TEAEs
- Incidence of serious TEAEs

- Common TEAEs (occurring in at least 5% of the total study population).

The summary of common TEAE will include 95% Newcombe confidence intervals for the differences in proportions between treatment arms.

In summaries including relationship to study treatment, the following relationships will be considered related: 'Definitely related', 'Probably Related', 'Possibly Related'. 'Unlikely to be Related' and 'Not related' will be considered unrelated.

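### The adverse event window follows each patient's own last dose, conflicts with daily collection to Day 35 for very early stoppers, and has no common cut-off in the between-arm TEAE comparison

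*Protocol*

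**What the plan says.** **The rule tied to last dose.** Protocol 7.7.1 sets the end of adverse event reporting: "All AEs and TEAEs will be reported from the day informed consent is obtained until 28 days after the last administration". Protocol 7.8 does the same for serious events: "All SAEs will be reported from the day informed consent is obtained until 28 days after the last administration". SAP 10.1 repeats the 28-day period.

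**The rule tied to Day 35.** For Days 29 to 35, Protocol 5.3.4 lists AEs and SAEs among the data that "should continue to be collected (as per Sections 7.7.1 and 7.7.2) on a daily basis until (and including) Day 35". Only in its separate block for Days 36 to 90 does it say "New AEs and SAEs will be collected up to 28 days after the last dose of study medication". Schedule footnote 8, attached to the AE row, keeps patients who stop dosing on these assessments where possible. Protocol 5.3.2 lists AEs and SAEs as key data for such patients, and 5.5 keeps patients withdrawn from medication only on the schedule to Day 90. Footnote 19, on the same AE row, refers back to 7.7.1 and 7.8.

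**The analysis.** SAP 10.1 summarises TEAEs by cumulative incidence and event counts, with "95% Newcombe confidence intervals for the differences in proportions between treatment arms". It gives no common cut-off day and no person-time adjustment.

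**The death endpoint.** SAP 5.3.1.5 identifies deaths first by an OSCI score of 8 up to Day 35, and additionally by "a fatal Adverse Event (AE) on or before Day 35 or withdrawal due to a fatal AE on or before Day 35".

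**Timing.** Under Protocol 8.11 the primary analysis is triggered when all patients have completed Day 35 or withdrawn. It includes every planned summary except those for Day 90.

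**The concern.** There are two separate problems.

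The first is a conflict between instructions. If a patient's last dose falls on Days 1 to 6, the 28-day clock runs out before Day 35. A new event after that point is outside 7.7.1 and 7.8 but inside the daily collection in 5.3.4. Because 5.3.4 and footnote 19 both point back to 7.7.1, sites could reasonably follow either rule, and different sites could follow different ones. For a randomised but undosed patient, 7.7.1 gives no end date at all.

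The second problem remains whichever rule is followed. The length of observation depends on when the patient stopped dosing, which happens after randomisation. Protocol 4.3.1 includes intolerable adverse events and inability to take the drug among the reasons for stopping, and footnote 8 gives becoming ventilated as an example. If SNG001 changes how many patients stop early, the arms are observed for different lengths of time. A crude difference in TEAE proportions then mixes drug effect with observation time. The arm with more early stoppers has its TEAE proportion understated.

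A related timing point concerns completers. Their new events are collected to Day 42 and documented at the next visit (Day 44 is the next one scheduled), but the primary analysis is triggered at Day 35. Events on Days 36 to 42 in the latest-enrolled patients may be incomplete in the primary safety tables.

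**Working it through.** The plan states no figure for this point, so there is nothing to reproduce.

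**Inputs.** Day 1 is the first dose and the last planned dose is Day 14 (Protocol 3, 5.3.1). The Safety population needs at least one dose (SAP 7.1.3), so the earliest possible last dose is Day 1. The collection tail is 28 days (Protocol 7.7.1, 7.8). The alternative floor is Day 35 (Protocol 5.3.4).

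**Step 1: window end by last-dose day d.** Under 7.7.1 alone the end is d + 28. With the 5.3.4 floor it is the larger of d + 28 and 35.

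| Last dose | 7.7.1 alone | With Day 35 floor | Days short of Day 35 under 7.7.1 alone |
|---|---|---|---|
| Day 1 | Day 29 | Day 35 | 6 |
| Day 3 | Day 31 | Day 35 | 4 |
| Day 6 | Day 34 | Day 35 | 1 |
| Day 7 | Day 35 | Day 35 | 0 |
| Day 14 | Day 42 | Day 42 | 0 |

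The two rules differ only for last doses on Days 1 to 6. The shortest window is 29/42 = 69% of a completer's under 7.7.1 alone, and 35/42 = 83% with the floor. The largest gap is 42 − 29 = 13 days or 42 − 35 = 7 days.

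**Step 2: average observation time.** Assume 20% of one arm and 10% of the other stop at Day 5 and the rest complete. Under 7.7.1 alone a Day 5 stopper loses 42 − 33 = 9 days, so the mean windows are 42 − 0.20 × 9 = 40.2 and 42 − 0.10 × 9 = 41.1 days. With the floor the loss is 7 days and the means are 40.6 and 41.3 days.

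**Step 3: effect on a crude TEAE difference.** The documents give neither TEAE risk nor stopping rates, so the following are assumptions: risk by Day 42 of 20%, 30% or 50%; one arm with 5 to 20 percentage points more patients stopping at Day 1; and the same event hazard in stoppers and completers. With constant hazard h = −ln(1 − p)/42, risk by day t is 1 − exp(−h·t).

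| Risk by Day 42 | By Day 29 | By Day 35 |
|---|---|---|
| 20% | 14.3% | 17.0% |
| 30% | 21.8% | 25.7% |
| 50% | 38.0% | 43.9% |

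The artefact is the excess share of early stoppers × (risk by Day 42 − risk by window end).

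- Window ending Day 29: from 0.05 × (20.0 − 14.3) = 0.3 points to 0.20 × (50.0 − 38.0) = 2.4 points.
- Window ending Day 35: from 0.05 × (20.0 − 17.0) = 0.15 points to 0.20 × (50.0 − 43.9) = 1.2 points.

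If instead the hazard falls to one quarter after Day 14, the ranges shrink to about 0.1 to 1.1 points (Day 29) and 0.1 to 0.6 points (Day 35).

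**Step 4: scale.** With 305 patients per arm and a 50% TEAE proportion, the half-width of a 95% interval for the difference is about 1.96 × √(2 × 0.5 × 0.5/305) = 7.9 points (simple large-sample approximation). The largest artefact above, 2.4 points, is under a third of that.

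**The case against.** The strongest reply is that 5.3.4 can be read as a coherent whole: everyone is followed daily to Day 35, and the last dose + 28 limit applies only from Day 36. Footnote 8, 5.3.2 and 5.5 support that reading. Much of this stands. A reader might infer that early stoppers are definitely covered only to Day 29, but the documents support that only as one of two readings. What does not stand is that the matter is settled. Sections 7.7.1 and 7.8 are unqualified, and both 5.3.4 and footnote 19 refer back to 7.7.1.

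A reader might also infer that deaths by Day 35 would be missed in the patients most likely to die. The documents do not support this. OSCI is recorded daily to Day 35 whatever the dosing status (Protocol 6.6). Deterioration leading to intensive care or invasive ventilation must be reported as an SAE (7.3). SAEs are followed to resolution even after the patient leaves the study (7.8), and death is recorded as the outcome of the causal SAE (7.7.2). A death could be lost only if a new fatal event began after the patient's window closed, no OSCI was recorded, and the daily collection to Day 35 was not applied.

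Nor do the documents show that patients stop mainly for tolerability or deterioration. Section 4.3.1 lists reasons without frequencies, and footnote 8 also allows any other reason.

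Other fair points are these. A fixed period after exposure is a legitimate design, and it captures late events in completers. The safety analysis is descriptive, with no hypothesis test. Undosed patients are outside the Safety population, so they cannot affect SAP 10.1; the missing end date matters only for SAE reporting and as a back-up source for the ITT death endpoint. SAP 7.4.1 describes the primary lock as following entry of all data for the primary and secondary endpoints, which include safety, and a follow-up analysis comes after Day 90. Incomplete Day 36 to 42 data at the primary analysis is therefore a possibility, not a certainty.

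**Conclusion.** The point holds as a drafting conflict together with a modest gap in the safety analysis. Sections 7.7.1 and 7.8 and SAP 10.1 cannot all be followed alongside 5.3.4 for last doses on Days 1 to 6, and the protocol does not say which governs. Whichever does, observation time varies with the time of stopping, by up to 13 days or up to 7 days, and the between-arm TEAE proportions have no common window.

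The likely effect is small: 0.15 to 2.4 percentage points under constant hazard with 5 to 20 points more Day 1 stoppers in one arm, and less if events cluster early. It is zero if early stopping is balanced and stoppers have the same event risk in both arms. These figures rest on assumed risks and stopping rates. They would be larger if early stoppers had a higher late-event risk than completers. The death endpoint is largely protected. This is a cheap improvement, not a threat to the trial's conclusions.

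**What to change.** **Protocol 7.7.1 and 7.8:** reconcile with 5.3.4 so that new AEs and SAEs are collected to at least Day 35 in every patient still in the study, counting from randomisation if the patient was never dosed, and on to 28 days after the last dose where that is later. Align the collection sentence in SAP 10.1.

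**SAP 10.1:** present the between-arm proportions for TEAEs, serious TEAEs and fatal TEAEs, with their Newcombe intervals, for events with onset from first dose to Day 35 in all Safety patients. Keep the planned full-window summary alongside, so that events on Days 36 to 42 stay visible, and note that this part may be incomplete at the primary analysis.

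**Cost:** wording changes in both documents and one more set of safety tables. No visits are added, because daily contact to Day 35 is already scheduled for patients who stop dosing, and Day 35 matches the primary analysis trigger.
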